- a) Could moisturiser with tocotrienol rich composition (REMDII[®] Sensitive, Malaysia) improve severity of atopic dermatitis of children with mild to moderate atopic dermatitis?
- b) What is the extend of baseline changes in IGA, SCORAD, IDLQI, PO-SCORAD, HR-USI, TEWL, skin color and pruritus score in children upon usage of REMDII[®] Sensitive?
- c) How well would children tolerate REMDII[®] Sensitive?

6. Research objectives and hypotheses

General objective

To assess the effectiveness and safety of a moisturiser containing tocotrienol rich composition (REMDII[®] Sensitive, Malaysia) on children with mild-to-moderate atopic dermatitis.

Specific objectives

- To assess the effectiveness and safety of REMDII[®] Sensitive as a supplement in mild-to-moderate atopic dermatitis in children based on the changes of IGA score and SCORAD.
- To assess correlation between patient-assessed PO-SCORAD and clinicianassessed IGA and SCORAD in children after 12 weeks of treatment using REMDII[®] Sensitive.
- To assess the changes in IDLQI.
- To assess the changes in patients' assessment of pruritus (based on a 100 mm Visual Analogue Scale and 0-3 ordinal scale).

- To assess the changes in skin properties, specifically high resolution ultrasound skin imaging (HR-USI), transepidermal water loss (TEWL) and skin color in children before and after application of REMDII[®] Sensitive.
- To assess the frequency of need for rescue medication in the event of an atopic dermatitis flare.

Hypotheses

Null: REMDII[®] Sensitive does not improve severity of atopic dermatitis of children with mild to moderate atopic dermatitis.

Alternative: REMDII[®] Sensitive significantly improves severity of atopic dermatitis of children with mild to moderate atopic dermatitis.

7. Literature review

Eczema is a general term used to describe numerous forms of epidermal inflammation or irritation that occurs regardless of gender, race and age. Among the various types of eczema, the most prevalent type is atopic dermatitis (AD). Currently, the prevalence rate of AD in children and adolescents was 15.0-20.0%, regardless of regions (Asher et al., 2006; Baek et al., 2013). Eczema poses significant impact and inconveniences to the patients' quality of life and health-care resources, mainly because of sleep deprivation and demoted self-esteemed (due to itchiness, scarring, lichenification, peer pressure and time to care), that would in turn affects the child's growth and development.

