9.1.3 Endpoints

Primary endpoint: Change from baseline the severity of atopic dermatitis – IGA score.

Secondary endpoints:

- Changes in SCORAD
- Changes from baseline the
 - IDQOL & CDLQI
 - PO-SCORAD
 - Pruritus score (VAS/ ordinal)
 - Frequency of rescue treatment needed
 - High resolution ultrasound skin-imaging (HR-USI), skin color & Transepidermal Water Loss (TEWL)
- Correlation between SCORAD index and PO-SCORAD or IDLQI at each baseline and follow-up visit and absolute changes from baseline.
- Efficacy and safety assessment of the study product.

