9.1.8 Sample Size

Sample size calculations were performed according to Cheon et al. (2013) using the following formula, where the mean difference and standard deviation of the scoring atopic dermatitis (SCORAD) index will be 10 and 13.576, respectively.

$$n = \frac{2(z_{\alpha/2} + z_{\beta})^2 \sigma^2}{(\mu_c - \mu_t)^2} = \frac{2 \times (1.96 + 0.84)^2 \times 13.576^2}{10^2} = 28.932$$

Using 80% power, a 5% significance level, and a 10% dropout rate, the required sample size will be corrected to approximately 33 participants for a group. Therefore, a total of 33 participants will be needed for this trial.

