9.2.8 Termination of Study

The sponsor may decide to terminate the study at any time. Subjects will be informed if the study is terminated and follow-up visits will be arranged if needed.

10. Statistical Analysis Plan

All data obtained at baseline will be given a coded ID-number before they are used in further statistical analyses.

- 10.1 The data analysis will be performed using Minitab 16. Descriptive date will be expressed as mean ± standard deviation (SD) unless otherwise stated. A value of P < 0.05 is considered statistically significant.
- 10.2 Prior to the statistical analysis, investigator needs to determine whether intention-to-treat analysis or modified intended-to-treat analysis is used for the statistical analysis. As well per-protocol analysis also can be carried out for comparison purpose. In

addition, the distribution of the data needs to be checked if it is following Gaussian distribution.

- 10.3 Comparison of SCORAD index between baseline and follow-up visits (if data is following Gaussian distribution, ANOVA will be used. If it is not following Gaussian distribution, Kruskal-Wallis test will be used.)
- 10.4 Comparison of POEM between baseline and follow-up visits (if data is following Gaussian distribution, ANOVA will be used. If it is not following Gaussian distribution, Kruskal-Wallis test will be used.)
- 10.5 Comparison of DLQI between baseline and follow-up visits (if data is following Gaussian distribution, ANOVA will be used. If it is not following Gaussian distribution, Kruskal-Wallis test will be used).
- 10.6 Correlation between SCORAD index with POEM or DLQI at baseline will be analysed using correlation coefficient (r) test. The cut-off values to interpret the correlations were as follows: < 0.5 = no correlation, > 0.5 = correlation, > 0.7 = high correlation. (If it is following Gaussian distribution, Pearson correlation will be used. If it is not following Gaussian distribution, Spearman correlation will be used)

11. Expected outcome

- REMDII[®] Sensitive will be effective in improving mild-to-moderate atopic dermatitis in children based on the positive changes of IGA score and SCORAD.
- Clinician-assessed IGA and SCORAD is directly correlated with patient-assessed SCORAD after 12 weeks of treatment using IP.
- IDLQI of subjects significantly improved compared to baseline as well as vehicle group.
- REMDII[®] Sensitive improves skin properties (HR-USI, color & TEWL) in children.

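### The planned correlation analysis (section 10.6) names other instruments and an earlier time point than the correlation objective and endpoint, and its label for r below 0.5 would report significant correlations as none

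*Protocol*

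**What the plan says.** The protocol describes the correlation analysis in four places.

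- Section 6, specific objectives: "To assess correlation between patient-assessed PO-SCORAD and clinicianassessed IGA and SCORAD in children after 12 weeks of treatment".
- Section 9.1.3, secondary endpoints: "Correlation between SCORAD index and PO-SCORAD or IDLQI at each baseline and follow-up visit and absolute changes from baseline".
- Section 11, expected outcome: "Clinician-assessed IGA and SCORAD is directly correlated with patient-assessed SCORAD after 12 weeks of treatment using IP".
- Section 10.6, the analysis itself: "Correlation between SCORAD index with POEM or DLQI at baseline will be analysed using correlation coefficient (r) test".

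Section 10.6 then grades the coefficient: "< 0.5 = no correlation, > 0.5 = correlation, > 0.7 = high correlation". Section 10.1 sets the significance rule for the whole plan: "A value of P < 0.05 is considered statistically significant".

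POEM occurs only in 10.4 and 10.6. PO-SCORAD and IGA do not occur anywhere in section 10. The visit procedures in 9.1.10 name IGA, SCORAD and DLQI.

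**The concern.** The analysis text does not deliver what the objective and endpoint promise. It replaces PO-SCORAD with POEM, leaves out IGA, and names baseline where the objective names week 12. An analyst who follows 10.6 would report something the trial did not set out to study. An analyst who follows section 6 or 9.1.3 would depart from the written analysis. Either way, the choice of instrument and visit would be made after the data are in.

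The grading adds a reporting problem. A coefficient that passes the plan's own significance test could be published as showing no relationship between the patient's and the clinician's view of severity.

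**Working it through.** **1. The passages side by side**

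| Place | Patient-side measure | Clinician measure | Time |
|---|---|---|---|
| Section 6, objective | PO-SCORAD | IGA, SCORAD | after 12 weeks |
| Section 11, expected outcome | patient-assessed SCORAD | IGA, SCORAD | after 12 weeks |
| Section 9.1.3, endpoint | PO-SCORAD or IDLQI | SCORAD | baseline, follow-up, change |
| Section 10.6, analysis | POEM or DLQI | SCORAD | baseline |

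The objective needs two correlations at week 12: PO-SCORAD with SCORAD, and PO-SCORAD with IGA. Section 10.6 supplies 0 of 2.

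The endpoint has two pairs (SCORAD with PO-SCORAD, SCORAD with IDLQI) and three kinds of time point (baseline, follow-up, change), so 2 × 3 = 6 cells. Section 10.6 supplies at most 1 of 6, the baseline SCORAD–quality-of-life cell, and only if DLQI there means IDLQI/CDLQI.

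**2. Number of children behind each r**

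Section 9.1.8 gives the inputs: "the mean difference and standard deviation of the scoring atopic dermatitis (SCORAD) index will be 10 and 13.576, respectively", and "Using 80% power, a 5% significance level, and a 10% dropout rate".

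- n = 2(z₁ + z₂)²σ²/δ². With the printed z values, 2 × (1.96 + 0.84)² × 13.576²/10² = 28.90. Unrounded z values give the stated 28.932. Both round up to 29.
- After dropout, 29/0.9 = 32.2, rounded up to 33. The plan's figure is reproduced.

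A baseline correlation would therefore rest on about 33 children, and a week-12 correlation on about 29 if dropout is as planned.

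**3. Where r becomes significant**

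Two-sided testing is assumed. The plan does not state the sidedness for correlations, but the 1.96 in the sample-size formula is two-sided. For Pearson's r, the critical value is t/√(n − 2 + t²), with t the 0.975 quantile on n − 2 degrees of freedom.

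- n = 33: t = 2.040, so 2.040/√(31 + 4.160) = 0.344.
- n = 29: t = 2.052, so 2.052/√(27 + 4.210) = 0.367.

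Spearman values are close at these sizes. Every r from 0.344 (or 0.367) up to 0.5 is therefore significant under 10.1 and 'no correlation' under 10.6.

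**4. Examples inside that band**

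- r = 0.45, n = 33: t = 0.45 × √(31/(1 − 0.45²)) = 2.81, P = 0.009. The Fisher-z 95% interval is 0.13 to 0.69.
- r = 0.49: P = 0.004 at n = 33 and 0.007 at n = 29.

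**5. Precision at the cut-off**

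At r = 0.5 the 95% interval is 0.19 to 0.72 (n = 33) or 0.16 to 0.73 (n = 29). A single cut at 0.5 on the point estimate cannot separate the categories reliably with this many children.

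**6. Limit of the band**

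The band applies where all children contribute to one r, as with PO-SCORAD. If IDLQI and CDLQI are analysed separately, each group is smaller. At n = 16, t = 2.145 and 2.145/√(14 + 4.601) = 0.497, so the band almost disappears there.

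**The case against.** The strongest reply has four parts.

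- **Baseline is not a wrong time.** Section 9.1.3 includes it, and 10.6 does not say 'only'. This stands: for the endpoint, 10.6 is incomplete in timing. For the objective, which is set at week 12, it still misses.
- **DLQI is probably shorthand.** Section 9.1.10.13 also uses DLQI for the questionnaire answered at each visit. This stands too, and that half is a naming problem. It does not rescue POEM, which has no counterpart among the objectives, endpoints or listed procedures.
- **Grading strength is separate from testing.** A P value tests whether the true correlation is zero, while the cut-offs grade size, so the two rules can coexist. This is correct. What remains is the wording: 'no correlation' asserts absence, where 'weak' would only describe size. This is a secondary defect and not a reason why the objective would fail.
- **A separate statistical analysis plan may settle the details.** That would answer an omission. Here the protocol states an analysis, under a heading that calls it the statistical analysis plan, and it conflicts with other sections.

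A reader might also infer that baseline is the worst time to correlate, because entry is limited to IGA 2 or 3 and a narrowed range lowers r. The documents do not support this. They give no spread of any score at any visit, selection is on IGA, body surface area and pruritus rather than on the correlated scores, and week-12 scores could bunch at the low end if children improve. Nor is it worth arguing that a strong negative r would be labelled as none, since section 11 expects a direct relationship.

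**Conclusion.** The contradiction is established from the text alone. Section 10.6 as written gives none of the objective's correlations and at most one of six parts of the endpoint. The labelling defect is real but smaller: it affects r between 0.344 and 0.5 with 33 children, or 0.367 and 0.5 with 29, assuming two-sided Pearson tests and the planned dropout.

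A reader might go further and conclude that the objective cannot be met. The documents do not show that. Section 9.1.3 independently commits to SCORAD with PO-SCORAD at the visits and for change, so the sections conflict and an amendment can reconcile them. The opposite assumption, that the data will be there in any case, is not shown either: the visit text does not list PO-SCORAD, and the flow chart is not available here. The matter concerns a secondary analysis and should be corrected before analysis starts.

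**What to change.** Rewrite 10.6 so that it:

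- correlates PO-SCORAD with SCORAD (Pearson or Spearman) and with IGA (Spearman, because IGA is ordinal) at week 12;
- correlates SCORAD with PO-SCORAD, and with IDLQI and CDLQI analysed separately, at baseline, at each follow-up visit and for change from baseline;
- removes POEM, or reconciles it with the objectives, endpoints and visit procedures (10.4 needs the same decision);
- uses one set of names for the quality-of-life questionnaires throughout the protocol;
- reports each r with its 95% confidence interval, and replaces 'no correlation' with a strength label such as 'weak'.

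Confirm that PO-SCORAD is scheduled at baseline and every follow-up visit. If it is, the cost is one rewritten paragraph and some consistent naming. If it is not, the visit schedule must be amended as well, and the correction becomes urgent because missed assessments cannot be recovered.

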9.1 Study Type and Design

9.1.1 Study design

A Phase 2, single arm, open label, single-centre trial will be conducted at Hospital Pengajar UPM, [name] and Lipidware Sdn. Bhd. Participants fulfilling the eligibility criteria will be selected. Each participant will be examined for signs and symptoms of AD before and after using REMDII[®] Sensitive. Figure 2 shows the outline of the study.

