9.1.2 Investigative product (IP)

Subjects will be provided with REMDII[®] Sensitive throughout the duration of the study.

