9.1.5 Inclusion Criteria

- **9.1.5.1** Male and female ages 1 month to 12 years with a diagnosis of atopic dermatitis based on UK Working Party Criteria of Atopic Dermatitis (Williams, Jburney, Pembroke, Hay, & Party, 1994).
- **9.1.5.2** Individuals with IGA score of at least mild (IGA= 2) or moderate (IGA= 3) and have at least 5% of body surface area affected during the inclusion time.
- **9.1.5.3** Individuals with a carer reported pruritus score based on VAS of at least 40 mm and above.
- **9.1.5.4** Individuals with no other chronic health condition other than atopic dermatitis e.g. asthma, allergic rhinitis or allergy.
- **9.1.5.5** Individuals with no objection towards use of topical corticosteroids as prescribed by attending medical officer during the study.
- **9.1.5.6** Written informed consent for participation in the trial.

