9.1.7 Withdrawal Criteria

The subjects who meet the criteria listed in Subject Withdrawal Criteria section will be discontinued from treatment or they may can choose to withdraw voluntarily at any time. Subjects may be withdrawn if the investigator deems that it is detrimental or risky for the subject to continue. All withdrawn subjects should attend the final study visit. Withdrawn subjects after randomization will not be replaced and will be followed for outcomes.

Subject Withdrawal Criteria

9.1.7.1 Patients with exacerbation which is not controlled by per protocol rescue medicine in 2 weeks.

9.1.7.2 Infection failed to be treated with per protocol oral antibiotic. Or those who develop cutaneous sepsis, as defined by skin infection + >/= 2 meets SIRS definition, as defined below:

9.1.7.2.1 Temp >38.5°C or > 36°C.

- 9.1.7.2.2 Tachycardia or bradycardia (if <1 year).
- 9.1.7.2.3 Tachypnea or requiring mechanical ventilation.
- 9.1.7.2.4 Abnormal leukocyte count or >10% bands.
- 9.1.7.3 Infection which are not deemed related to atopic eczema <i.e pneumonia, UTI, AGE, will not be withdrawn even if fulfilled sepsis criteria.
- 9.1.7.4 The development of any severe adverse event, as defined by the Malaysian GCP.
- 9.1.7.5 Use of any forbidden medication or treatment, and/or other use moisturisers or emollients during the trial that could affect the study result.
- 9.1.7.6 Subjects who did not comply with the protocol of at least two times-per-day application of cream.
- 9.1.7.7 Subject's withdrawal of consent.
- 9.1.7.8 Detection of eligibility violations, occurrence of other significant protocol violations during the trial.
- 9.1.7.9 Investigator's decision to terminate the process for the sake of the subject's health.
- 9.1.7.10 Dropouts are defined as patients who did not attend for follow-up visit within the designated visit window (+/- 3 days) and whose outcomes are unknown by the end of the trial.

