9.1.10 Study Visits and Procedures

- 9.1.10.1 Subjects who are eligible to take part in this trial will need to attend to the study site for a total of 5 compulsory visits, as illustrated in Fig. 3.
- 9.1.10.2 During the screening/baseline visit, it will take about 1 hours where the investigators will take note of the subjects conditions for evaluation of study acceptability.
- 9.1.10.3 Prior to any baseline measurement, the correct usage of the cream will be explained by the investigator and the investigator's team. Subjects will be required to apply at least 1 fingertip unit to 2% body surface area. The subjects will receive treatment with the IP for topical application for 3 times a day for 12 weeks (according to the guideline that emphasize the important of using sufficient emollient).
- 9.1.10.4 Subjects will be provided with non-soap-based shower product (REMDII® Calming Body Wash, Malaysia) for subject's shower purpose throughout

the study. Subjects should avoid the usage of soap-based products throughout the study.

- 9.1.10.5 Subjects will also be provided with a diary, for recording of any application of rescue treatment and deviation from the study protocols.
- 9.1.10.6 Subjects who have flare up, will be managed using hydrocortisone 1% cream for a duration of 7 days. Those who are not responding to hydrocortisone end of 7 days will be prescribed with clobetasone butyrate 0.05% cream for additional 7 days. Those who doesn't respond to the treatment shall be withdrawn. However, subjects need to record the application in the provided diary. As well, any deviation or illness that occurs during the study will need to be recorded in the same diary as well.
- 9.1.10.7 Those who acquired secondary bacterial infection will be treated with a week of cloxacillin (50-100mg/kg/day po in 4 divided dose). For those who are above 20kg, will receive the usual adult dose.
- 9.1.10.8 In patients with penicillin allergy will be given a week of erythromycin ethylsuccinate at a dose of 30mg/kg/day in divided dose (up to a max 2gm/day).
- 9.1.10.9 Patients who have eczema herpeticum will received a week of oral acyclovir, in which subjects 1 month till 2 years will receive 100mg 5×/day; while subjects age 2 to 12 years old will received 200mg 5×/day dosage.
- 9.1.10.10After the explanation of the "Dos and Don'ts" to the guardians/parents, baseline measurement of atopic dermatitis severity of subjects using SCORAD index will be conducted.

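### The protocol expects improvement over a vehicle group that this single-arm trial does not have, and it credits the product with a before-after change that its design cannot attribute to it

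*Protocol*

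**What the plan says.** Protocol Section 11 lists as an expected result: "IDLQI of subjects significantly improved compared to baseline as well as vehicle group". Section 9.1.7 states: "Withdrawn subjects after randomization will not be replaced". Section 9.1.1, in line with the title, says: "A Phase 2, single arm, open label, single-centre trial will be conducted". Section 9.1.2 supplies the product to subjects "throughout the duration of the study". No vehicle, placebo or other control arm is defined anywhere.

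The alternative hypothesis in Section 6 is that the product "significantly improves severity of atopic dermatitis of children with mild to moderate atopic dermatitis", and Section 11 expects it to be effective on IGA and SCORAD. The comparisons over time in Section 10 (SCORAD, POEM, DLQI) are all baseline against follow-up visits.

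Other influences apply over the same 12 weeks:
- Section 9.1.10.4: "Subjects will be provided with non-soap-based shower product", and soap-based products are to be avoided.
- Section 9.1.10.6: children who flare are treated with topical corticosteroid.
- Section 9.1.5.3 admits: "Individuals with a carer reported pruritus score based on VAS of at least 40 mm and above". Section 9.1.3 lists the pruritus score as a secondary endpoint.

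**The concern.** There are two linked problems. First, one stated outcome needs a comparator that the trial does not contain. No analysis plan can supply a missing arm, so this is not a detail that could be settled later.

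Second, the hypothesis concerns what the product does, but the contrast that would test it is change over time in treated children. Such a change combines the product, the supplied wash, steroid given for flares, the natural course of the disease, open-label assessment and the effect of selecting children on their symptoms. If the null is rejected, the protocol as written would conclude that the product improves atopic dermatitis. The data would support only that children on this regimen changed.

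**Working it through.** **1. Comparator.** Expected outcome (Section 11): baseline and vehicle. Design (title, 9.1.1): one arm, open label. Treatment (9.1.2): the product only. Analyses (Section 10): baseline against follow-up. The vehicle contrast appears in none of the objectives, endpoints or analyses. The reference to randomization in 9.1.7 likewise has no event to attach to.

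**2. The plan's own sample size, for context.** Section 9.1.8 uses n = 2(z_α/2 + z_β)²σ²/(μ_c − μ_t)² with difference 10 and SD 13.576 on SCORAD.
- Printed z values: 2 × (1.96 + 0.84)² × 13.576² / 100 = 28.90. Unrounded z values give 28.93, matching the stated 28.932.
- Rounded up, 29; allowing for 10% dropout, 29/0.9 = 32.2, so 33.

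This reproduces. The formula gives the size of each of two independent groups. On these inputs a real vehicle comparison would need 2 × 33 = 66 children, and the planned total is 33. The enrolled number is therefore no evidence that a second arm was provided for.

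**3. Attribution.** Write the mean change from baseline as product effect + wash + rescue steroid + natural course + open-label assessment + selection at entry. With one arm, only the sum is observed. A test that the sum is zero does not test that the first term is zero.

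**4. Selection on itch.** Children enter only if the VAS is at least 40 mm. If source-population scores are normal with mean μ and SD σ, and the correlation between two measurements is r, the expected fall on remeasurement with no treatment effect is

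fall = (1 − r) × σ × λ, with a = (40 − μ)/σ and λ = φ(a)/(1 − Φ(a)).

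The protocol gives none of μ, σ or r. The values below are assumptions chosen to span a plausible range.

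| μ (mm) | σ (mm) | r | a | λ | Fall (mm) |
|---|---|---|---|---|---|
| 40 | 25 | 0.5 | 0 | 0.798 | 0.5 × 25 × 0.798 = 10.0 |
| 50 | 20 | 0.7 | −0.5 | 0.509 | 0.3 × 20 × 0.509 = 3.1 |
| 60 | 15 | 0.8 | −1.33 | 0.180 | 0.2 × 15 × 0.180 = 0.5 |

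Over μ 40 to 60, σ 15 to 25 and r 0.5 to 0.8, the fall runs from about 0.5 to 10 mm. The direction is determined; the size is not.

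**5. IGA.** Section 9.1.5.2 requires IGA 2 or 3 and 9.1.6.2 excludes 4. Entry is cut at both ends, so even the direction of regression to the mean is not fixed for the primary endpoint. The itch calculation does not carry over to it.

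**The case against.** A single-arm, open-label phase II trial is a legitimate design, and the protocol states it openly. Research question (b) asks for the extent of change from baseline, the endpoints are mostly changes from baseline, and rescue use is both an endpoint and recorded in a diary. The vehicle phrase is one bullet in a list of expectations, and no analysis depends on it. All of this stands. The lack of a control arm is not the fault. The fault lies in wording that claims a comparison and a cause the design cannot deliver.

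Some stronger readings are tempting but unsupported:
- **Every child receives steroid.** Sections 9.1.5.5 and 9.1.6.7 make willingness to use corticosteroid a condition of entry, but 9.1.10.6 gives rescue only to those who flare.
- **Every child switches to a new wash.** The protocol says only that a wash is supplied and soap avoided. It does not record what was used before.
- **An inert product would often be declared effective on itch.** Simulating 29 children with source mean 40 to 50 mm, SD 20 and r 0.6 to 0.8, a paired t-test finds significant improvement in about 14 to 50% of trials, against a nominal 2.5%. Section 10 names no test for pruritus, however, and no paired test at all. On the same inputs, a one-way ANOVA over five visits (the number in 9.1.10.1), with equal correlation between visits, is significant in about 0 to 11%. With a source mean of 60 mm (SD 15 to 20), the paired rate is about 4 to 10%. These rates rest on assumed inputs and concern one secondary endpoint, so they do not measure this trial's error rate.

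**Conclusion.** The point holds as a contradiction in the text and an over-claim. The vehicle comparison cannot be made, and the reference to randomization describes an event that does not occur; neither conclusion needs any assumption. It also follows from the design alone that a significant change from baseline would not establish the product's own effect.

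The size of the non-product contribution cannot be derived from the protocol. For itch, selection at entry is expected to produce some apparent improvement, about 0.5 to 10 mm on the assumed normal model and input ranges. No corresponding figure can be given for IGA. The matter should be corrected because it changes what the trial may conclude. It does not invalidate the trial as a single-arm study.

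**What to change.** - **Section 11:** delete the vehicle group as a comparator in the IDLQI expectation.
- **Section 9.1.7:** replace the reference to randomization with a point that exists in this design, such as enrolment.
- **Sections 6 and 11:** restate the hypotheses and expectations as mean change from baseline to week 12 under the whole study regimen (product, supplied body wash and permitted rescue), reported with a 95% CI. State that the trial does not establish the product's own effect.
- **Sections 9.1.3 and 10:** label the pruritus VAS change as descriptive, because the same score is an entry criterion.

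These are wording changes in five places. They need no new visit, procedure or participant. The downside is a more modest claim.
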